APPENDIX 3. OVERVIEW OF RESEARCH SITES

21

GLOSSARY OF ABBREVIATIONS

CLOCS	Cancer Loyalty Card Study
HSR1	High Street Retailer 1
HSR2	High Street Retailer 2

KEYWORDS

Ovarian Cancer
Epidemiology
Observational Study
Risk Assessment

STUDY SUMMARY

TITLE Cancer Loyalty Card Study (CLOCS)

DESIGN Observational, retrospective case-control study

AIMS The CLOCS aims to investigate whether or not women have distinctive self-management behaviours prior to seeing their doctor with symptoms that are associated with ovarian cancer.

OUTCOME MEASURES The primary outcome of the CLOCS will be to define the time by which the cases and controls are statistically significantly different in their purchase behaviours leading up to diagnosis on a population level.

The secondary outcome of the CLOCS will be defining a purchase threshold as an “alert” about cancer symptoms in individuals and determining the predictive utility of purchasing behaviours in the early detection of ovarian cancer. Exploratory analyses will include longitudinal analyses, frequency of purchases and an unbiased analysis of other purchase categories.

POPULATION At least 1000 women in the UK (500 ovarian cancer cases and 500 controls)

ELIGIBILITY Women, at least 18 years old, who own at least one participating high street retailer loyalty card are eligible to join the CLOCS. Among these women, those who have been diagnosed with ovarian cancer can join the CLOCS as cases, and those who have no prior ovarian cancer diagnosis are eligible to join as controls.

DURATION 3 years

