3.1 STUDY OUTCOME MEASURES

We aim to detect significant changes in purchase behaviours of ovarian cancer patients prior to diagnosis, and potentially improve the sensitivity of detection of cancer “alert symptoms” by stratifying the analysis on risk profiles, cancer stage or histology.

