9.2 Data analysis

- 9.2.1 The statistical software R will be used for all data analyses.
- 9.2.2 We will define the time prior to diagnosis by which the cases become statistically significantly different in their purchase behaviours to the controls.
- 9.2.3 We will explore this using a multivariable, conditional logistic regression model with ovarian cancer as the outcome and "purchase proportion" at different times prior to diagnosis as the exposure, adjusting for stage and histology and other potentially confounding variables collected from the risk factor questionnaire.
- 9.2.4 We will compare the proportions of purchases in cases to controls, stratified by risk quintiles defined by the epidemiological risk model (estimated n=86 per quintile) or by histology (with expected proportions of high grade serous cases n=335; mucinous cases n=70; endometrioid n=35; clear cell n=35, and low grade serous n=25).
- 9.2.5 We will estimate the predictive values (ROC AUC, PPV, NPV, specificity and sensitivity) of this "early diagnosis" test for each stratum.
- 9.2.6 We will conduct exploratory analyses investigating other methods leveraging the auto correlation in the longitudinal data. Specifically, we will investigate the frequency of purchases and purchase trajectories, to identify purchase patterns (e.g. increasing purchases before diagnosis, purchase peaks, etc.), that are indicative/predictive of the individual disease onset.

- 9.2.7** Using longitudinal approaches, we will investigate if these patterns help in predicting the time-to-onset.
- 9.2.8** This type of approach could be generalised using other purchase categories for further hypothesis generation.

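### Sections 9.2.4–9.2.5 analyse risk and histology strata one at a time with no test of whether the strata differ, so they cannot show that stratifying improves detection

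*Combined protocol and SAP*

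**What the plan says.** Section 9.2.4 plans case-control comparisons of purchase proportions within strata. One stratification uses risk: "We will compare the proportions of purchases in cases to controls, stratified by risk quintiles defined by the epidemiological risk model (estimated n=86 per quintile"). The other uses histology, with expected counts of "high grade serous cases n=335; mucinous cases n=70; endometrioid n=35; clear cell n=35, and low grade serous n=25". The two are joined by *or*, so the plan may mean one of them or both. Section 9.2.5 adds ROC AUC, PPV, NPV, sensitivity and specificity for each stratum.

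Section 3.1, headed Study Outcome Measures, gives the purpose. Besides detecting significant changes in purchasing, the study hopes to "potentially improve the sensitivity of detection of cancer “alert symptoms” by stratifying the analysis on risk profiles, cancer stage or histology".

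Two places say what is exploratory. The Study Summary states: "Exploratory analyses will include longitudinal analyses, frequency of purchases and an unbiased analysis of other purchase categories". In section 9.2 the word is attached to the longitudinal, frequency and trajectory work that starts at 9.2.6, after the stratified comparisons. Neither place mentions strata.

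The documents give no alpha, no interaction or heterogeneity test, no statement that strata are for estimation only, and no rule for reading a set of stratum results together.

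**The concern.** The question in section 3.1 is comparative: does purchasing behaviour, or its value for detection, differ between risk groups or histologies enough for stratifying to help? The stated analyses answer a different question, namely what each stratum shows by itself. A result in one stratum and none in another does not show that the two differ, particularly when one has 335 cases and the other 25.

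There are two practical consequences. If strata are judged by significance, the chance that at least one looks positive under no effect is well above the per-test level. If they are judged by accuracy, the best of several noisy AUCs will on average exceed the whole-sample AUC even when every stratum is identical. Either could be taken as support for section 3.1, and could then carry over into the secondary aim of a purchase threshold that serves as an alert.

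**Working it through.** **Inputs from the documents.** At least 500 cases and 500 controls (Study Summary); five quintiles of 86 and histology counts 335, 70, 35, 35 and 25 (9.2.4).

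**Assumptions, not in the documents.** Two-sided 0.05 per stratum; a single time point; a true AUC of 0.60 in every stratum, chosen only for illustration.

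**The plan's own figures.** 335 + 70 + 35 + 35 + 25 = 500, which matches the case target. The quintile size does not follow from it: 500/5 = 100, while 5 × 86 = 430. The figure 86 equals (500 − 70)/5, which would fit leaving mucinous cases out, but the documents do not say so. This is a separate point and does not drive the results below.

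**Step 1. Chance of at least one false stratum signal, no true effect anywhere.** For k independent tests at level a it is 1 − (1 − a)^k.

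- One stratification, k = 5: 1 − 0.95^5 = 0.226.
- Both, k = 10, if independent: 1 − 0.95^10 = 0.401.
- Both, allowing for the same women being split two ways: 0.37–0.39 by simulation (20,000 replicates per setting). This range covers normal and binary (30%) outcomes, controls divided with their matched cases or all shared across histologies, and mucinous cases kept in or left out of the quintiles.

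Because alpha is unstated, the ten-stratum range matters: about 0.095 at a per-test level of 0.01 (0.096 if independent) and about 0.62 at 0.10 (0.651 if independent). Several time points (9.2.3), or stage strata (named in 3.1), would raise these figures.

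**Step 2. Accuracy of the best stratum when all are equal.** The Hanley–McNeil variance for AUC A with n cases and m controls is [A(1 − A) + (n − 1)(q1 − A²) + (m − 1)(q2 − A²)]/(nm), with q1 = A/(2 − A) and q2 = 2A²/(1 + A). For A = 0.60, q1 = 0.4286, q2 = 0.45 and A² = 0.36. Against all 500 controls:

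- n = 335: (0.24 + 334 × 0.0686 + 499 × 0.09)/167,500 = 0.000406, so SE = 0.020.
- n = 25: (0.24 + 24 × 0.0686 + 499 × 0.09)/12,500 = 0.00374, so SE = 0.061.

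The smallest stratum's AUC is about three times as variable as the largest's, so taking the maximum favours chance highs. In 3,000 simulated studies with true AUC 0.60 in every histology:

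| Quantity | Mean |
|---|---|
| Whole-sample AUC | 0.60 |
| Best histology AUC, each against all controls | 0.65 |
| Best histology AUC, equal-sized control groups | 0.67 |

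The apparent gain of 0.05–0.07 is selection, not better detection.

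**Step 3. What a global test does.** One heterogeneity test per stratification replaces five separate readings. At 0.05 each, the chance of any false claim of difference is 0.05 with one stratification and about 1 − 0.95² = 0.098 with both, treating the two tests as independent.

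**The case against.** The strongest reply is that the plan never says what a critic would have it say. Most of this stands, and it limits the point.

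- **Status of the strata.** A reader might infer from section 3.1 that ten subgroup comparisons are study outcomes. The documents do not support that. The primary and secondary outcomes in the Study Summary and section 2 mention no strata, 3.1 speaks only of a potential improvement, and the Summary's exploratory list need not be exhaustive. The strata are unlabelled, not declared confirmatory.
- **Testing.** Section 9.2.4 says: "We will compare the proportions of purchases in cases to controls". Section 9.2.5 speaks of estimating. Statistical significance is attached to the primary aim. So it would be too strong to say that about 4 in 10 studies run to this plan would report a false stratum signal. That needs stratum p-values, a 0.05 threshold and both stratifications, none of which is fixed. With one stratification the figure is about 0.23.
- **Pattern of results.** A reader might expect a common true effect to appear as a signal in high grade serous disease and none in the other types. Under an assumed common effect of 0.2 SD of the paired difference, simulated power is 0.948, 0.368, 0.201, 0.221 and 0.164 in the order listed in 9.2.4. That exact pattern then has probability 0.948 × 0.632 × 0.799 × 0.779 × 0.836 = 0.31, so it is not the expected result.
- **Stratum size.** Nor can one say without condition that significance will mostly follow stratum size. Under no effect, every stratum has the same 5% chance.
- **Formal adjustment.** Multiplicity adjustment is often not used in observational work of this kind, and the point does not require it.

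What the reply does not answer is that 3.1 raises a question about differences between strata and section 9.2 contains no analysis that addresses it.

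**Conclusion.** The point holds in limited form. Separate stratum comparisons and a best-stratum AUC cannot show that histologies or risk groups differ, or that stratifying improves detection, and the plan offers nothing else for that purpose. The chance of at least one false stratum signal is about 0.23 for one stratification and 0.38–0.40 for both, conditional on testing each stratum at an assumed two-sided 0.05 at one time point. The selection effect on the best histology AUC is about 0.05–0.07, conditional on an illustrative true AUC of 0.60 throughout. Neither figure forecasts what the study will report. They show how far stratum-by-stratum reading can mislead. The whole-sample primary comparison is not affected by this point.

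**What to change.** In 9.2.4–9.2.5, and in the Study Summary's exploratory list:

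1. Label the risk-quintile and histology analyses exploratory, and say whether one stratification or both will be used.
2. Report each stratum's case-control difference and each accuracy measure with a confidence interval.
3. Base any claim that purchasing differs by histology or risk group on one global heterogeneity test per stratification, with its level stated. For histology, which controls do not have, a case-only or polytomous comparison of the purchase effect would serve. For risk, use a purchase-by-quintile interaction.
4. State that the best stratum's accuracy will not be used as evidence that stratifying improves detection.

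The cost is protocol wording and one or two extra tests on data already being collected, with no further participants. The downside is that a result in a single stratum becomes hypothesis-generating, and a global test may have little power to detect a difference confined to the small histologies.

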1. INTRODUCTION

1.1 BACKGROUND

The ten-year survival rate for epithelial ovarian cancer (EOC) is only 35% in the UK and is dramatically different for stage 1 disease (90%) compared with stage 3-4 (5-15%). Survival in the UK lags behind Europe; this is attributed partly to a delay in diagnosis [1]. Earlier detection of low-volume disease or earlier stage ovarian cancer will save lives [2].

EOC is a heterogeneous disease with different histological subtypes that show strikingly different molecular [3] and mutational profiles [4,5]. With the Ovarian

Cancer Association Consortium (OCAC), we have identified 34 common genetic polymorphisms contributing to polygenic risk [6–9]. Epidemiological risk factors provide a predictive model with a modest discriminatory power (AUC=0.65), improved slightly with polygenic risk (AUC=0.66) [10], and this model has been proposed to improve EOC detection with risk stratified screening [11].

EOC usually presents with vague and non-alarming symptoms. As a result, most women are diagnosed late when the cancer has already spread and the prognosis is poor. The most common symptoms associated with EOC are increased abdominal size, pelvic pain, abdominal pain and bloating, feeling full quickly and difficulty eating [12,13]. The major reasons for not presenting to the GP with symptoms such as these are “not wanting to waste the GP’s time” [14] and normalisation of these symptoms [15]. The persistence of a symptom, social influence and awareness encourage help-seeking behaviours in primary care [16]. However, few believe that their symptom(s) might be a sign of cancer [17]. Consequently, people might choose to self-manage their symptoms by using over-the-counter medication, and to seek advice from other sources, (pharmacists, family, internet), rather than a primary care physician.

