3. STUDY DESIGN

Purpose and Design

The Cancer Loyalty Card Study (CLOCS) is addressing whether or not data already collected by high street retailers can detect significant changes in purchase behaviours of ovarian cancer patients prior to their diagnosis. We aim to conduct a case-control study of ovarian cancer patients matched with women who do not have ovarian cancer. We will recruit at least 500 recently diagnosed ovarian cancer patients and at least 500 healthy women as controls and collate up to 6 years of prior purchase data.

Recruitment

Women living with ovarian cancer and who own at least one of the participating high street retailer's loyalty cards will be recruited in a clinic by a member of their healthcare team where the study is open (recruitment sites listed in Part C).

Women, 18 years or older, living in the UK who have a loyalty card at the participating high street retailers will be recruited through the study website (www.clocsproject.org.uk) where data collection will be safeguarded using an encrypted web form that includes study consent and the self-report questionnaire. There will be a press release and social media about the study inviting loyalty card holders to visit the CLOCS website for more information and join the study. Any woman considering joining the study can contact the research team using the contact details on the information sheet.

Consent

Ovarian cancer patients will be given the information sheet and consent form in the clinic by a member of their healthcare team. They can take as much time as they need to read through the information sheet. If they choose to participate, they can complete the consent form whenever is convenient for them and return it to the CLOCS team in the freepost envelope provided to them in the clinic.

Alternative recruitment strategy during Covid-19 lockdown to minimise contact with patients

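### Predictive accuracy is planned only within strata: no analysis gives overall accuracy, combines purchases with the risk score in one prediction, or tests whether purchase effects differ by risk

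*Combined protocol and SAP*

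**What the plan says.** Section 3.1 hopes to "potentially improve the sensitivity of detection of cancer" alert symptoms, and names the means: "stratifying the analysis on risk profiles, cancer stage or histology". The secondary aim in 2.2 is an individual alert threshold and the predictive utility of purchases. Section 1.1 gives a benchmark: "Epidemiological risk factors provide a predictive model with a modest discriminatory power (AUC=0.65".

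Four items of section 9.2 bear on this:

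- 9.2.3 is a multivariable conditional logistic regression of case status on purchase proportion. It is not restricted to strata and adjusts for stage, histology and potential confounders from the questionnaire.
- 9.2.4 compares purchase proportions between cases and controls, "stratified by risk quintiles defined by the epidemiological risk model (estimated n=86 per quintile", or by histology.
- 9.2.5 reads "We will estimate the predictive values (ROC AUC, PPV, NPV, specificity and sensitivity) of this" early-diagnosis test, for each stratum.
- 9.2.6 and 9.2.7 are exploratory longitudinal analyses of purchase patterns.

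The planned sample is "At least 1000 women in the UK (500 ovarian cancer cases and 500 controls", in a matched design. Neither the matching factors nor the ratio is given.

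**The concern.** The hope in 3.1 and the secondary aim raise a question of added value: how much better is an alert that uses both purchases and risk than one that uses either alone? The planned accuracy output does not answer it. Within a risk quintile the score varies little, so a stratum AUC or sensitivity describes mainly purchases. No planned estimate covers all women, no prediction puts the score and purchases together, and no single test asks whether the strata differ.

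Two misreadings become possible. If purchases and risk carry independent information, the quintile AUCs will be about equal, and that flat row could be taken to mean that risk adds little. Conversely, chance differences among five imprecise AUCs could be read as a risk gradient, with no heterogeneity test to check them.

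**Working it through.** **The plan's own figure.** 500/5 = 100 and 1000/5 = 200, so 86 per quintile does not follow from the sample size. 86 × 5 = 430, which is 86% of 500. The histology counts sum to 335 + 70 + 35 + 35 + 25 = 500, and 500 − 70 = 430. That fits leaving out the mucinous cases, but equally leaving out endometrioid plus clear cell (35 + 35), or a 14% loss. The plan states none of these, and does not say whether 86 counts cases, pairs or women. Both sizes are therefore carried below.

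**Precision of a stratum AUC.** Hanley–McNeil: SE² = [A(1−A) + (n₁−1)(Q₁−A²) + (n₂−1)(Q₂−A²)]/(n₁n₂), with Q₁ = A/(2−A) and Q₂ = 2A²/(1+A). The AUC is assumed, since the documents give no purchase effect. At A = 0.70, Q₁ = 0.5385, Q₂ = 0.5765 and A² = 0.49.

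| Cases / controls | SE | 95% half-width (1.96 × SE) |
|---|---|---|
| 43 / 43 (86 women in total) | 0.0564 | 0.111 |
| 86 / 86 | 0.0397 | 0.078 |
| 430 / 430 | 0.0177 | 0.035 |
| 500 / 500 | 0.0164 | 0.032 |

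At 86/86, one quintile is 0.078/0.035 = 2.2 times less precise than 430/430 and 0.078/0.032 = 2.4 times less precise than 500/500. A difference between two such quintile AUCs has half-width 1.96 × √2 × 0.0397 = 0.110.

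**What combining could add.** Inputs: risk AUC 0.65 (section 1.1); purchase AUC 0.60 to 0.70 (assumed); both binormal and independent given case status (assumed). Separation d = √2 × z(AUC); combined d = √(d_risk² + d_purchase²); AUC = Φ(d/√2); sensitivity at 95% specificity = Φ(d − 1.645).

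- Risk alone: d = √2 × z(0.65) = 0.545; sensitivity Φ(−1.100) = 14%.
- Purchase AUC 0.60: d = 0.358, sensitivity Φ(−1.287) = 10%. Combined d = √(0.297 + 0.128) = 0.652, AUC 0.678, sensitivity Φ(−0.993) = 16%.
- Purchase AUC 0.70: d = 0.742, sensitivity Φ(−0.903) = 18%. Combined d = √(0.297 + 0.550) = 0.920, AUC 0.742, sensitivity Φ(−0.725) = 23%.

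In a simulation of the 0.70 case with quintile cuts from the pooled sample, the purchase AUC inside every quintile is 0.70 to within simulation error (0.698 to 0.702). The gain from 0.70 to 0.742 leaves no trace in the stratum AUCs.

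**Matched pairs (conditional).** Suppose 1:1 pairs are kept inside quintiles and matching is not on risk. With risk AUC 0.65, simulation puts both members in the same quintile for about 19-20% of pairs at within-pair risk correlation 0, 24-26% at 0.3, 29-30% at 0.5 and 38-39% at 0.8. About 60-80% of pairs would then be split.

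**The case against.** Several stronger readings are tempting, and the documents do not support them.

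- *Purchases are assessed only inside risk quintiles.* Not so. Section 9.2.3 covers the whole sample and can include questionnaire risk factors alongside purchases; 9.2.4 also stratifies by histology; 9.2.6 and 9.2.7 are not confined to strata. What remains is that 9.2.3 is an association model with risk factors as confounders and names no accuracy measure, while the exploratory items name neither the risk score nor an accuracy measure.
- *Section 3.1 makes a claim that cannot be tested.* It says only that stratifying might potentially help. The data to be collected would permit the test; the plan does not specify it.
- *The study would conclude that risk profiling adds nothing.* This looks at AUC alone, whereas 9.2.5 also plans PPV. In the same set-up with 1:1 sampling, the case share runs from 63/200 = 31.5% in the lowest quintile to 137/200 = 68.5% in the highest. At 95% specificity, PPV then rises from (0.315 × 0.183)/(0.315 × 0.183 + 0.685 × 0.05) = 0.63 to 0.89. Absent matching on risk, that gradient would appear in the planned output. It would show that risk matters, but not the gain in AUC or sensitivity from combining.
- *Quintiles discard the risk information.* Mostly not. With purchase AUC 0.70, a rule using purchases plus quintile membership reaches AUC 0.739 and about 23% sensitivity, close to the continuous score. With 0.60 it reaches 15% against 16%. What is missing is a pooling step; stratifying is not in itself a defect.
- *The split wastes matched pairs.* That requires a paired comparison within quintiles and matching not on risk, and the plan states neither. If the comparison is unpaired, no pairs are lost, but the matching is ignored.

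It is also fair to object that equal groups of 86 are a simplification. With pooled cuts and 430 of each, the lowest quintile would hold about 54 cases and 118 controls and the highest the reverse. At AUC 0.70 the formula above gives half-widths of 0.088 and 0.079, so the order of magnitude stands.

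**Conclusion.** The point holds as an omission. Accuracy is specified only by stratum, so the hope in 3.1 and the secondary aim have no analysis that answers them directly. Stratum AUCs and sensitivities cannot measure what risk adds to purchases, or what purchases add to a model with AUC 0.65.

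The loss of precision follows from the stratum size and depends on what 86 counts. The possible gain from combining is illustrative only: it rests on an assumed purchase AUC and on independence given case status, and it would shrink if matching removed risk differences between cases and controls. The splitting of pairs is conditional, as stated above. The primary aim is not affected. This should be corrected because it bears on a secondary aim and the remedy costs almost nothing.

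**What to change.** - **9.2.4:** add one model over all women with purchase exposure, the risk score (preferably continuous) and their product, with a single heterogeneity test. Keep the quintile tables as description. State what 86 counts and how it was reached, and whether the within-quintile comparison keeps the pairing.
- **9.2.5:** add whole-sample AUC and sensitivity at a fixed high specificity for (1) risk score alone, (2) purchases alone and (3) both. Report the differences (3)−(2) and (3)−(1), with bootstrap intervals resampled by matched set.
- **Matching:** name the matching factors, and note that any risk-score component used for matching cannot be evaluated.

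The cost is a change of wording and a little more analysis work on questionnaire and purchase data already to be collected. Recruitment is unaffected.

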1.2 RATIONALE FOR CURRENT STUDY

Approximately 7,400 new cases of ovarian cancer are diagnosed each year in the UK, and with over 4,000 women dying from the disease each year it is a particularly lethal form of cancer. The symptoms are not well known, are vague and non-specific and most women are diagnosed at a late stage when the cancer has already spread around the peritoneum with poor prognosis. Novel methods are needed to improve earlier detection and thereby improve survival from this disease. We hypothesise that a change in purchasing behaviour, primarily an increase in self-medication to treat these vague cancer symptoms, may provide a novel avenue for earlier diagnosis for cancer.

In this study we propose to use loyalty card data from two participating high street retailers (Boots and Tesco) to investigate purchase behaviour as an opportunity for cancer symptom surveillance. We aim to conduct a case-control study of women with ovarian cancer (cases) matched with women who do not have ovarian cancer (controls) and define the time by which the cases are statistically significantly different in their purchase behaviours leading up to date of diagnosis, compared with the control purchase behaviours.

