2. STUDY OBJECTIVES

- 2.1** The primary aim of the CLOCS will be to define the time by which participants with ovarian cancer are statistically significantly different in their purchase behaviours leading up to date of diagnosis, compared with purchase behaviours of participants without ovarian cancer.
- 2.2** The secondary aim of the CLOCS will be to define a purchase threshold as an “alert” about cancer symptoms in individuals and determining the predictive utility of purchasing behaviours in the early detection of ovarian cancer.

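### Section 9.2.5 plans PPV and NPV per stratum in a case-control sample without an estimation method, an external incidence or a defined alert period; a direct sample estimate would be badly wrong

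*Combined protocol and SAP*

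**What the plan says.** The secondary aim (Section 2.2) is an individual purchase threshold that works as an alert, and "determining the predictive utility of purchasing behaviours in the early detection of ovarian cancer". For this, 9.2.5 states: "We will estimate the predictive values (ROC AUC, PPV, NPV, specificity and sensitivity", for an early-diagnosis test in each stratum. The strata come from 9.2.4: risk quintiles, or histology "with expected proportions of high grade serous cases n=335; mucinous cases n=70; endometrioid n=35; clear cell n=35, and low grade serous n=25".

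Recruitment fixes the make-up of the sample. Section 3 plans "at least 500 recently diagnosed ovarian cancer patients and at least 500 healthy women as controls", and the Study Summary gives the same counts. Section 1.2 describes a "case-control study of women with ovarian cancer (cases) matched with women who do not have ovarian cancer (controls", and 9.2.3 uses a "multivariable, conditional logistic regression model with ovarian cancer as the outcome". No matching ratio is stated.

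Section 9.2 names no incidence or prevalence, no reweighting and no Bayes step. The only incidence-type figure is background in Section 1.2: "Approximately 7,400 new cases of ovarian cancer are diagnosed each year in the UK". It has no population denominator, and 9.2 does not use it. Section 9.2.2 will produce a time before diagnosis at which cases and controls diverge, but 9.2.5 does not link that time to the predictive values.

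**The concern.** Sensitivity is a property of the cases and specificity of the controls, so neither depends on how many of each are recruited. The same holds for AUC. PPV and NPV depend on the share of women who have, or will soon be diagnosed with, the disease. Here that share is set by recruitment. Section 9.2.5 lists all five measures together and draws no distinction.

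PPV is the figure a reader would use to judge an alert, because it says what an alert means for the woman who receives it. A value reflecting a sample that is about half cases would make the alert look far more informative than it could be among loyalty-card holders in general.

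Histology strata add a second difficulty. Controls have no histology, and the plan does not say which controls are compared with each subtype. The case share in each stratum is therefore undefined.

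**Working it through.** The plan states no PPV, NPV, sensitivity or specificity, so there is no figure to reproduce. The histology counts sum to 335 + 70 + 35 + 35 + 25 = 500, the planned number of cases, which confirms that they count cases only.

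**Inputs from the documents:** 500 cases and 500 controls (Study Summary; Section 3, as minima); the histology counts (9.2.4); 7,400 UK cases a year (1.2).

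**Assumptions:** sensitivity (Se) 50% and specificity (Sp) 90%, for illustration; 20 to 30 million women at risk; a one-year horizon.

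**Formulas,** with p the case share:

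- PPV = Se·p / [Se·p + (1 − Sp)(1 − p)]
- NPV = Sp(1 − p) / [Sp(1 − p) + (1 − Se)p]

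**Step 1: direct estimate at 1:1, p = 0.5.**

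- PPV = 0.25 / (0.25 + 0.05) = 83.3%
- NPV = 0.45 / (0.45 + 0.25) = 64.3%

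**Step 2: the same test at an external one-year incidence.**

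- 20 million women: p = 7,400 / 20,000,000 = 0.037%. PPV = 0.000185 / (0.000185 + 0.099963) = 0.18%. NPV = 0.899667 / (0.899667 + 0.000185) = 99.98%.
- 30 million women: p = 0.0247%. PPV = 0.000123 / (0.000123 + 0.099975) = 0.12%. NPV = 99.99%.

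**Step 3: does the gap survive kinder assumptions?** At specificity 99%, the sample PPV is 0.5 / (0.5 + 0.01) = 98.0%, against 1.2% to 1.8% over one year. Now take a group at an assumed five times the average incidence, followed for five years with sensitivity unchanged. Then p = 7,400 × 5 × 5 / N = 0.62% to 0.93% and PPV is 24% to 32%, still far below 98.0%.

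**Step 4: only if all controls are used, not fixed-ratio matched sets.** At 50%/90%, the sample PPV is 83.3% at 1:1, 0.5 / (0.5 + 0.2) = 71.4% at 1:2, and 0.5 / (0.5 + 0.4) = 55.6% at 1:4. By histology, PPV = 0.5n / (0.5n + 0.1 × 500):

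| Cases in stratum | Case share n/(n + 500) | PPV, all 500 controls | PPV, 1:1 matched |
|---|---|---|---|
| 335 | 40.1% | 77.0% | 83.3% |
| 70 | 12.3% | 41.2% | 83.3% |
| 35 | 6.5% | 25.9% | 83.3% |
| 25 | 4.8% | 20.0% | 83.3% |

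The test is identical in every row. Against all controls, PPV falls through stratum size alone. With 1:1 matched sets that spread disappears, but the distortion between Steps 1 and 2 remains.

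**The case against.** Four points on the other side have force.

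**No wrong formula is stated.** A reader might infer that 9.2.5 prescribes taking PPV and NPV from the sample. It does not; it is silent on method, and the sponsor may intend a Bayes calculation. This stands, and the point is therefore conditional. It is still more than missing detail, because the most direct way to carry out the sentence gives an invalid answer and the documents contain none of the inputs for a valid one.

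**Time is not ignored.** A reader might infer that the plan has no time frame for an alert. In fact the divergence time is the primary output, and it can reasonably be a result and not a pre-set input. What remains is that nothing says how it becomes the period over which PPV is defined.

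**Matching may protect against part of this.** A reader might infer that PPV must move with control sign-up and stratum size. With fixed-ratio matched sets it would not, and matching is how the study is described. Since no ratio or comparator is given, the other branch stays open but should not be presumed.

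**Most magnitude inputs are assumed.** True: only the case and control counts, the histology counts and the 7,400 come from the documents. The conclusion survives the range tried.

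A reader might also take 500:500 as assurance that choosing window and threshold in the same data does little harm. The documents do not support that: 9.2.5 reports by stratum, one with 25 expected cases, and does not say whether those choices are made overall or within strata.

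**Conclusion.** The point holds as a specification gap whose default reading is invalid, and it should be fixed before the analysis. If PPV and NPV are computed directly from the sample, PPV will be far too high and NPV too low for women who might receive an alert. In the base illustration PPV is overstated by a factor of about 450 to 680 (83.3/0.185 to 83.3/0.123). The exact figures rest on the assumed sensitivity, specificity, population and horizon; the direction does not, so long as the target population has a far smaller case share than the sample. Dependence on control numbers and on histology stratum size is a further artefact that arises only if all controls are used. AUC, sensitivity and specificity do not depend on the recruitment ratio, and the primary outcome is not affected.

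**What to change.** Amend 9.2.5 as follows.

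- Estimate AUC, sensitivity and specificity from the sample.
- Compute PPV and NPV by Bayes' rule at a cited external incidence, age-specific and, for quintiles, risk-specific. State the alert horizon and how it derives from the time found under 9.2.2. Show results over a range of incidence and specificity. Otherwise drop PPV and NPV.
- For histology, report sensitivity by subtype against a stated control set. Give PPV only for ovarian cancer overall, since histology is unknown when an alert fires.
- State that specificity comes from self-selected website volunteers who passed ID checks (5.1, 5.1.1), in a design described as matched, and may not transfer to the target population. Bayes' rule does not cure this.
- Report bootstrap or cross-validated accuracy with matched sets kept together, repeating the choice of window and threshold in each resample.

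The cost is SAP wording, a short calculation and some resampling code; no new participants or participant data are needed. The downside is that the reported PPV becomes much less favourable, and an incidence source and a horizon must be chosen and defended.
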